5.3 Other Study Related Definitions

Analytical Study Week Assignments

Analytical windows will be used to assign parameter measurements to study weeks. The algorithm is provided in [Appendix A](#).

Actual Treatment Group

A subject's actual treatment group is the randomized treatment group, unless the subject receives treatment throughout the study that is different than the randomized treatment group assignment, in which case the actual treatment group is the treatment received.

Investigational Product (IP)

Olpasiran SC 10 mg Q12W, 75 mg Q12W, 225 mg Q12W, 225 mg Q24W and placebo SC Q12W.

Study Exposure Period in Months

For each randomized subject, Study Exposure Period = (EOS date – Randomization Date + 1) / 365.25 * 12

IP Exposure Period in Months

IP Exposure Period = [min (Last IP Dose Date + 84 days, EOS Date) – First IP Dose Date + 1] / 365.25 * 12

Treatment Emergent Adverse Event in Treatment Period

Events categorized as Adverse Events (AEs) starting on or after first dose of investigational product as determined by “Did event start before first dose of investigational product” equal to No or missing on the Events eCRF and up to the End of Treatment Period date, or EOS date for subjects who early discontinue the study during the treatment period.

Treatment Emergent Adverse Event in Extended Safety Follow-up Period

Events categorized as Adverse Events (AEs) starting on or after first dose of investigational product (as determined by “Did event start before first dose of

investigational product” equal to No or missing on the Events eCRF) and on or after the Extended Safety Follow-up Period Start Date, and up to the EOS date.

Reflexive Approach for LDL-C and VLDL-C

Reflexive approach for LDL-C and VLDL-C is only applicable for the central lab data. For all analyses related to LDL-C and VLDL-C, unless specified otherwise, the following reflexive approach will be used.

When calculated LDL-C is less than 40 mg/dL or triglycerides are > 400 mg/dL, the ultracentrifugation (UC) LDL-C value from the same blood sample will be used instead of calculated LDL-C and the UC VLDL-C value from the same blood sample will be used instead of calculated VLDL-C, if available.

6. Analysis Sets

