2.1 Study Rationale

Study 20180109 is a double-blind, randomized, multicenter dose finding study in subjects with atherosclerotic cardiovascular disease and elevated lipoprotein(a) (Lp[a]). The primary objective is to test olpasiran administered subcutaneous (SC) **once** every 12 weeks (Q12W) compared with placebo on percent change from baseline in Lp(a) after 36 weeks of treatment. Additionally, an exploratory dose of 225 mg **once** every 24 weeks (Q24W) will be evaluated. The treatment period is 48-weeks, with the last dose of investigational product administered at week 36. **After** the week 48 treatment period **there will be** an extended safety follow-up **for a minimum** of **24** weeks.

Olpasiran is being developed for the treatment of patients with atherosclerotic cardiovascular disease and elevated lipoprotein(a) (Lp[a]) to reduce the risk of cardiovascular events. Lp(a) reductions of $\geq 80\%$ from baseline are anticipated with olpasiran and it is expected that this level of reduction in Lp(a) may result in clinically meaningful cardiovascular benefit in patients with atherosclerotic cardiovascular disease (Kamstrup et al, 2009, Burgess et al, 2018, Lamina et al, 2019, Madsen et al, 2020).

Available data from the initial cohorts of the first in human (FIH) study has shown the following:

- Olpasiran can effectively lower Lp(a) levels.
- Pharmacodynamic (PD) effects last up to at least 3 months.
- At single doses up to 225 mg (cohort 7), olpasiran was tolerated with no safety concerns identified as of day 225.

The olpasiran target population is patients with atherosclerotic cardiovascular disease and significantly elevated Lp(a). All patients will be receiving optimized standard of care for other cardiovascular risk factors, including elevated low-density lipoprotein cholesterol (LDL-C), but still be at risk for cardiovascular events from high Lp(a) levels.

The Lp(a) cutoff of 150 nmol/L is based on the epidemiological data that is available showing that Lp(a) > 125 nmol/L is considered elevated from the general population data (Averna et al, 2017; Nordestgaard and Langsted, 2016; Ohro-Melander, 2015; Leebmann et al, 2013). In addition, based on the degree of absolute Lp(a) reduction necessary to demonstrate a corresponding effect on cardiovascular events, the enrolled population would need to have high baseline Lp(a). Therefore, an enrollment criterion of

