9.3 Analysis Sets, Subgroups, and Covariates

9.3.1 Analysis Sets

Full Analysis Sets (FAS): FAS includes all randomized subjects who received at least one dose of investigational product and will be used to perform the efficacy analysis based on randomized treatment group.

For safety analysis, FAS will be used based on the actual treatment received.

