6.1 Full Analysis Set

Full analysis set (FAS) includes all randomized subjects who received at least one dose of investigational product.

FAS will be used to perform the efficacy analysis based on randomized treatment group, and the safety analysis based on actual treatment group (defined in section 5.3).

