9.1 General Considerations

Unless specified otherwise, efficacy analyses will be performed on the FAS by randomized treatment group, and safety analyses will be performed on the FAS by actual treatment group.

For the Primary Analysis (as described in Section 7.2), all data up to the primary analysis data cut-off date will be included. Based on the snapshot for the primary analysis, efficacy and safety analyses will be performed. Testing will be performed for endpoints defined up to week 36. Descriptive summary will be provided for all available visits by period (ie. Treatment period and extended safety follow-up period).

For the End of Treatment Period Analysis (as described in Section 7.3), all data up to the end of treatment period analysis cut-off date will be included. Testing will be performed for endpoints defined up to week 48. Descriptive summary will be provided for all available visits by period (ie. Treatment period and extended safety follow-up period).

For the Final analysis (as described in Section 7.4), all efficacy and safety analyses during the extended follow-up period will be performed based on the snapshot for the final analysis.

Subject disposition, demographics, baseline characteristics, and exposure to IP will be summarized.

All categorical variables will be summarized using the number and percent of subjects and all continuous variables will be summarized using mean, standard error or standard deviation, median, minimum, maximum, and number of subjects with observations.

Multiplicity Adjustment Method:

The Hochberg procedure will be used to control the type I error for multiple comparisons between active and placebo groups in the primary endpoint. The primary endpoint includes percent change in Lp(a) from baseline at week 36 for olpasiran SC Q12W groups and placebo. Percent change in Lp(a) from baseline for Q24W group is defined as exploratory endpoint.

A summary of the analyses for each planned analysis can be found in Table 2.

Table 2. Summary of Analyses

Analyses	Primary Analysis (all data up to primary analysis data cut-off date)	End of Treatment Period Analysis (all data up to End of Treatment Period Analysis data cut-off date)	Final Analysis (all data based on final snapshot)

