9.6 Safety Analyses

9.6.1 Adverse Events

The Medical Dictionary for Regulatory Activities (MedDRA) version 24.0 or later will be used to code all events categorized as adverse events to a system organ class and a preferred term. All adverse event tables will be summarized by actual treatment group. All adverse event summaries will include all treatment-emergent events reported on the Event eCRF, including CEC reviewed events.

The subject incidence of adverse events will be summarized for all treatment-emergent adverse events, serious adverse events, adverse events leading to withdrawal of investigational product, and fatal adverse events.

Subject incidence of all treatment-emergent adverse events will be provided by preferred term in descending order of frequency. Treatment-emergent adverse events and treatment-emergent serious adverse events will be tabulated by system organ class, high level term, and preferred term in descending order of frequency. Treatment-emergent adverse events leading to discontinuation of investigational product, treatment-emergent fatal adverse events, treatment-related treatment-emergent adverse events, and treatment-related treatment-emergent serious adverse events will be provided by system organ class, and preferred term in descending order of frequency.

Subject incidence of adverse events of interest (peripheral neuropathy, myopathy, hypersensitivity reactions, effects on renal and liver function, hyperglycemia (including new onset diabetes), thrombocytopenia, coagulation parameters, immune-inflammatory and injection site reactions) will be summarized by category and preferred term.

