9.7 Other Analyses

9.7.1 Analyses of Pharmacokinetic or Pharmacokinetic/Pharmacodynamic Endpoints

A PK sub-study will be conducted with a total of approximately 75 subjects (approximately 15 from each treatment cohort). A maximum of 3 samples may be collected at additional time points during the study if warranted and agreed upon between the investigator and

the sponsor. Pharmacokinetic samples will be collected as per the PK sub-study schedule of assessments (see protocol Table 1-1 and Table 1-2).

Individual and summary statistics for PK concentrations will be provided. These analyses will be performed by the CPMS group for the primary analysis, the end of treatment period analysis, and final analysis.

10. Changes From Protocol-specified Analyses

There are no changes to the protocol-specified analyses.

11. Literature Citations / References

Grundy SM, Stone NJ, Bailey AL, et al.

AHA/ACC/AACVPR/AAPA/ABC/ACPM/ADA/AGS/APhA/ASPC/NLA/PCNA guideline on the management of blood cholesterol: a report of the American College of Cardiology/American Heart Association Task Force on Clinical Practice Guidelines. *Circulation*. 2018; 139: e1046-e1081.

Dinko Rekic, Yaning Wang, Vikram Sinha. Request for Qualification of MCP-Mod as an efficient statistical methodology for model-based design and analysis of Phase II dose finding studies under model uncertainty. 22 April, 2015

12. Prioritization of Analyses

Not applicable.

13. Data Not Covered by This Plan

Not applicable.

14. Appendices

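### A placebo subject given olpasiran at some, but not all, dosing visits is still counted as placebo in the safety tables

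*SAP*

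**What the plan says.** SAP 5.3 defines the actual treatment group as the randomized group "unless the subject receives treatment throughout the study that is different than the randomized treatment group assignment". Only a subject who meets that condition is moved to the group of the treatment given. SAP 6.1 adopts this definition for the safety analysis. SAP 9.1 repeats that "safety analyses will be performed on the FAS by actual treatment group", and SAP 9.6.1 adds: "All adverse event tables will be summarized by actual treatment group".

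Protocol 9.3.1 is shorter: "For safety analysis, FAS will be used based on the actual treatment received". It does not require the different treatment to have been given throughout. SAP section 10 declares: "There are no changes to the protocol-specified analyses".

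Two other statements bear on how long a dose matters. Protocol 2.1 reports from the first-in-human study that "Pharmacodynamic (PD) effects last up to at least 3 months". SAP 5.3 runs the IP exposure period to 84 days after the last dose, or to the end-of-study date if that is sooner.

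**The concern.** Grouping safety by actual treatment is meant to keep subjects who were exposed to the drug out of the control column. With four dosing occasions (day 1 and weeks 12, 24 and 36), an error at a single visit is an obvious way for treatment to go wrong: placebo comes in identical containers, and some olpasiran arms receive placebo to keep the blind (Protocol Table 6-1). The SAP rule deals only with a subject who was wrongly treated throughout.

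At stake is an adverse event in an olpasiran-exposed subject being tabulated under placebo. That raises the comparator rate and narrows the safety contrast. Efficacy is not affected, because it is analysed by randomized group.

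**Working it through.** **The plan's own safety figure.** SAP 3.2 gives 95% confidence of detecting one case at an incidence of 1/60, from 192 active-arm subjects with 5% drop-out.
- 192 × 0.95 = 182.4, taken as 182.
- P(at least one case) = 1 − (59/60)^182 = 95.3%. The stated figure is reproduced.

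**Which dosing errors the rule catches.** Take a placebo subject who receives all four injections, each either correct or wrong.
- Patterns with at least one wrong dose: 2^4 − 1 = 15.
- Patterns that are wrong throughout: 1 (all four).
- Patterns that leave the subject in the placebo column: 15 − 1 = 14.

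This counts patterns; it says nothing about how likely each one is.

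**How much of the treatment period one dose covers.** The SAP's exposure definition adds 84 days after the last dose. 84/7 = 12 weeks, and 12/48 = 25% of the treatment period.

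**Effect on the placebo incidence.** The number of mis-dosed subjects is an assumption, since the documents give none. If k placebo subjects are partly mis-dosed and each has the event, the placebo incidence gains k/n.

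| k | n = 58 (planned enrolment) | n = 48 (sample-size minimum) |
|---|---|---|
| 0 | 0 | 0 |
| 1 | 1.7 points | 2.1 points |
| 2 | 3.4 points | 4.2 points |
| 3 | 5.2 points | 6.3 points |

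A mis-dosed subject without the event adds nothing to the numerator.

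**Effect on the detection figure.** Counting 1 to 3 such subjects as olpasiran-exposed gives 1 − (59/60)^183 = 95.4%, rising to 1 − (59/60)^185 = 95.5%. The sizing statement is essentially unchanged; what matters is the column in which a single case appears.

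**Whether another provision covers the gap.** SAP 8.4 tabulates important deviations likely to affect the efficacy endpoints. SAP 9.3 describes deviation categories and COVID-19 listings. Neither regroups partly mis-dosed subjects for safety or lists their events.

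**The case against.** The case for leaving the rule alone has several parts.

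- **Rarity.** Site staff give and document each injection (Protocol 6.5), box numbers are recorded (Protocol Table 6-1), and box ID lists go to the analysis team (SAP 8.2). Errors should be few and traceable. This stands, and it is why the point is minor. Traceability does not itself put the subject in the right column.
- **Conflict with the protocol.** A reader might infer that the SAP contradicts the protocol and that its statement of no changes is false. The documents do not clearly support that. The protocol never says how to classify a subject with mixed treatment, so SAP 5.3 can be read as filling a gap, although it fills it narrowly.
- **The Q24W arm.** A reader might infer that a Q24W subject given active drug at every visit stays in Q24W because only half the injections were wrong. SAP 5.3 names treatments as regimens, so that subject can equally be read as having received 225 mg Q12W throughout, and would then be moved.
- **Duration.** A reader might take the modelled 88% median reduction on 225 mg Q24W (Protocol 4.3) to mean that one stray dose covers 24 weeks. That figure is for repeated dosing at 225 mg. Moreover, the duration of Lp(a) lowering is not shown to be a window of adverse-event risk.
- **Other analyses.** The safety tables are not the only place where real exposure counts. The exposure-response analysis (Protocol 6.4.2.2 and Appendix 1) uses individual PK exposure and may include safety endpoints. It does not replace the adverse event tables.
- **The alternative has its own bias.** Moving every subject to the highest dose received would put largely unexposed time into the high-dose arms and could not separate the two 225 mg groups. This stands, and the remedy should be narrower.

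**Conclusion.** The point holds for a placebo subject given olpasiran at some but not all visits: the SAP leaves that subject in the safety control column. It does not hold for a placebo subject given olpasiran at every visit, who is moved. For a subject who stops early the rule is unclear, because *throughout* is not defined; someone whose only dose was wrong could be read either way.

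The size depends on a mis-dosing rate that the documents do not give. It is nil with no errors, and about 1.7 points of placebo incidence for each affected subject who has the event, at 58 per arm. Nothing in the documents ties the rule to short-acting drugs or shows that it was chosen for them. The case rests only on the wording, the reported effect of at least 3 months and the SAP's own 84-day exposure window. Severity is minor.

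**What to change.** Amend SAP 5.3 before unblinding, because placing such subjects afterwards would be a data-driven choice:

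- A subject randomized to placebo who receives any olpasiran is not summarized as placebo for safety. The subject is summarized under olpasiran, in the dose group received, with a pre-specified tie-break between 225 mg Q12W and 225 mg Q24W and a stated rule for anyone who received more than one dose level.
- A subject randomized to olpasiran stays in the randomized group unless the regimen actually received matches another group.
- Every subject with any incorrect administration is listed, with dates and with events before and after the first incorrect dose.

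The cost is a few sentences and one listing, and the box-number data are already collected. The drawback is that a reassigned subject's events before exposure are attributed to olpasiran; the listing makes this visible.

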8.2.4.1.2 Serious Adverse Events

The investigator is responsible for ensuring that all serious adverse events observed by the investigator or reported by the subject that occur after signing of the informed consent through **EOS** are reported using the Events CRF.

All serious adverse events will be collected, recorded and reported to the sponsor or designee within 24 hours of the investigator's knowledge of the event, as indicated in

Section 11.4. The investigator will submit any updated serious adverse event data to the sponsor within 24 hours of it being available.

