Subjects may be eligible for continued treatment with Amgen investigational product(s) by an extension protocol or as provided for by the local country's regulatory mechanism. However, Amgen reserves the unilateral right, at its sole discretion, to determine whether to supply Amgen investigational product(s) and by what mechanism, after termination of the study and before the product(s) is/are available commercially.

Compensation

Any arrangements for compensation to subjects for injury or illness that arises in the study are described in the Compensation for Injury section of the Informed Consent that is available as a separate document.

11.4 Appendix 4. Safety Events: Definitions and Procedures for Recording, Evaluating, Follow-up, and Reporting

Definition of Adverse Event

Adverse Event Definition

• An adverse event is any untoward medical occurrence in a clinical study subject irrespective of a causal relationship with the study treatment.• Note: An adverse event can therefore be any unfavorable and unintended sign (including an abnormal laboratory finding), symptom, or disease (new or exacerbated) temporally associated with the use of a treatment, combination product, medical device or procedure.• Note: Treatment-emergent adverse events will be defined in the Statistical Analysis Plan (SAP).

Events Meeting the Adverse Event Definition

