The detection and documentation procedures for adverse device effects described in this protocol apply to all Non-Amgen medical devices provided for use in the study (see Section 6.1.2 for the list of Non-Amgen medical devices).

Adverse Device Effect Definition

An adverse device effect is any adverse event related to the use of a combination product or medical device. Adverse device effects include, but are not limited to, adverse events resulting from insufficient or inadequate instructions for use, adverse events resulting from any malfunction of the device, or adverse events resulting from use error or from intentional misuse of the device.

Recording Adverse Events and Serious Adverse Events

Adverse Event and Serious Adverse Event Recording

- When an adverse event or serious adverse event occurs, it is the responsibility of the investigator to review all documentation (eg, hospital progress notes, laboratory, and diagnostics reports) related to the event.
- The investigator will then record all relevant adverse event/serious adverse event information in the Event case report form (CRF).
- The investigator must assign the following adverse event attributes:
 - Adverse event diagnosis or syndrome(s), if known (if not known, signs or symptoms);
 - Dates of onset and resolution (if resolved);
 - Did the event start prior to first dose of investigational product, other protocol-required therapies;
 - Assessment of seriousness;
 - Severity (or toxicity defined below);
 - Assessment of relatedness to investigational product (**olpasiran/placebo**) **and/or other protocol-required therapies**;
 - Action taken, and
 - Outcome of event.
- If the severity of an adverse event changes from the date of onset to the date of resolution, record as a single event with the worst severity on the Events CRF.
- It is not acceptable for the investigator to send photocopies of the subject's medical records to Amgen in lieu of completion of the Events CRF page.
- If specifically requested, the investigator may need to provide additional follow-up information, such as discharge summaries, medical records, or extracts from the medical records. In this case, all subject identifiers, with the exception of the subject number, will be blinded on the copies of the medical records before submission to Amgen.

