- **Once the study has ended, serious adverse event(s) suspected to be related to investigational product will be reported to Amgen if the investigator becomes aware of a serious adverse event. The investigator should use the paper-based Serious Adverse Event Contingency Report Form to report the event.**

Figure 11-1. Sample Electronic Serious Adverse Event Contingency Form

Completion Instructions - Electronic Adverse Event Contingency Report Form (For use for clinical trial studies using Electronic Data Capture [EDC])

NOTE: This form is to be used under restricted conditions outlined on page 1 below. If you must fax an event report to Amgen, you must also enter that event into the EDC system (eg, Rave) when it becomes available.

General Instructions

The protocol will provide instruction on what types of events to report for the study. This form is to be used ONLY to report events that must be captured in the Amgen safety database. *Indicates a mandatory field.

Types of Events to be reported on this form

- Serious Adverse Events (regardless of causal relationship to IP)

1. Site Information

Site Number* – Enter your assigned site number for this study

Investigator*, Country*, Reporter*, Phone No., and Fax No. – Enter information requested

2. Subject Information

Subject ID Number* – Enter the entire number assigned to the subject

Age at event onset, Sex, and Race – Enter the subject's demographic information

End of Study date – If the subject has already completed the study or terminated the study early, enter the End of Study date

If you are submitting follow-up information to a previous report, provide the serious adverse event term for the previous report as well as the start date for the initial event.

3. Serious Adverse Event

Provide the date the investigator became aware of this information

Serious Adverse Event Diagnosis or Syndrome* –

- > If the diagnosis is known, it should be entered. Do not list all signs/symptoms if they are included in the diagnosis.
- > If a diagnosis is not known, the relevant signs/symptoms should be entered.
- > If the event is fatal, the cause of death should be entered and autopsy results should be submitted, when available.

Date Started* – Enter date the adverse event first started (not the date on which the event met serious criteria) rather than the date of diagnosis or hospitalization. **This is a mandatory field.**

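### The TEAE definition has no worsening clause, so an adverse event already recorded before first dose that becomes more severe or serious on treatment is left out of the TEAE tables

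*SAP*

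**What the plan says.** Protocol 11.4 leaves the definition to the SAP: "Treatment-emergent adverse events will be defined in the Statistical Analysis Plan (SAP"). SAP 5.3 then gives two definitions, one per period.

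- **Treatment period:** "Events categorized as Adverse Events (AEs) starting on or after first dose of investigational product as determined by" the start-before-first-dose question being "equal to No or missing on the Events eCRF and up to the End of Treatment Period date" (or the end-of-study date for early withdrawals).
- **Extended safety follow-up:** the same onset condition, and the event must also start on or after the follow-up start date.

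Neither definition mentions an increase in severity or a change to serious.

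Protocol 11.4 sets the recording rules. The investigator answers "Did the event start prior to first dose of investigational product, other protocol-required therapies"; no item asks about worsening after first dose. If severity changes, the site is to "record as a single event with the worst severity on the Events CRF". Follow-up information goes onto the CRF entry already completed for that event. The instructions for the SAE contingency form in Figure 11-1 say "Enter date the adverse event first started (not the date on which the event met serious criteria").

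SAP 9.6.1 builds its AE summaries on treatment-emergent events. The tables by system organ class and preferred term (all, serious, fatal, treatment-related, leading to discontinuation) are named as treatment-emergent.

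**The concern.** Each rule is ordinary by itself. Together they lose information: the database holds a worst severity reached on treatment, but the record is classified by an onset before treatment, so the TEAE tables drop it.

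TEAEs are the first-listed safety endpoint. The gap matters most for events with no other planned summary. Peripheral neuropathy and myopathy are AEs of interest in SAP 9.6.1. Protocol 8.2.1.4.1 sends abnormalities found at the neurological and muscular examination to the AE form. SAP Appendix A gives that examination visit windows, but SAP 9.6 describes no summary of it, so the AE tables are where such worsening would be seen.

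The same logic applies at the boundary between the two periods. An AE open at the End of Treatment Period Date that becomes serious later keeps its treatment-period onset and cannot enter the follow-up TEAE tables.

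**Working it through.** **1. The plan's own AE figure.** Protocol 9.2 and SAP 3.2 give 95% confidence of detecting one case at incidence 1/60, with 48 per arm in four active arms and 5% drop-out.

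- n = 4 × 48 × 0.95 = 182.4, taken as 182. P(at least one case) = 1 − (59/60)^182 = 95.3%.
- Without drop-out: 1 − (59/60)^192 = 96.0%.

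The figure reproduces. The point below is about definitions and does not change it.

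**2. The SAP 5.3 rule applied literally to test records.** Treatment period ends on day 337 (week 48) and study on day 505 (week 72), the scheduled days in SAP Appendix A.

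| Record | Started before first dose? | Classification |
|---|---|---|
| AE starts day −3, mild; severe on day 40; one record | Yes | Not a TEAE in either period |
| AE starts day 1 before dosing; serious on day 60; one record | Yes | Not a TEAE in either period |
| First record again, question unanswered | Missing | Treatment-period TEAE |
| Medical-history condition; exacerbation on day 40 entered as a new AE | No | Treatment-period TEAE |
| AE starts week 40 (day 7 × 40 + 1 = 281); serious at week 60 (day 421); one record | No | Treatment-period TEAE only |

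**3. How wide the pre-dose window is.**

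- Protocol Table 1-1 marks adverse events from day 1 pre-dose, with no mark at screening. Serious adverse events are marked at screening.
- Protocol 8.2.4.1.1 collects AEs after enrollment; 8.2.4.1.2 collects SAEs "that occur after signing of the informed consent through" end of study.
- Protocol 5.4 defines enrollment as the investigator's decision that eligibility is met. Appendix 1 (11.1) defines it as the day the consent form is signed.
- First dose is on the day of randomization (8.1.2); screening lasts up to 28 days (8.1.1).

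Under Table 1-1 and section 5.4 the window for non-serious AEs is short, essentially day 1 before dosing. Under Appendix 1 it could reach the length of screening. For SAEs it runs from consent on either reading.

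**4. The follow-up boundary.** SAP 9.1, Table 2, summarizes safety by period at the primary and end-of-treatment analyses, but at the final analysis only in the extended follow-up period. Take the last test record. If the event becomes serious before the end-of-treatment data cut-off, it is in the treatment-period serious-TEAE table. If it does so after that cut-off, it was non-serious in the end-of-treatment tables and is outside the follow-up TEAE tables at the final analysis. No planned serious-TEAE table then clearly contains it.

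**5. Scale, as illustration only.** The documents give no share of cases that would go uncounted. If a share m of cases of a 1/60 event were lost, P = 1 − (1 − (1 − m)/60)^182. This gives 95.2% for m = 1%, 94.5% for 5%, 93.6% for 10% and 91.3% for 20%. At the planned 58 per arm, n = 4 × 58 × 0.95 = 220.4, and the figures are 97.5% with no loss and 94.8% with m = 20%.

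**The case against.** The strongest reply is that few events can fall into the gap.

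- **Medical history.** Protocol 8.2.1.3 sends conditions through day 1 to medical history and names peripheral neuropathy and transient liver test abnormalities. Protocol 11.4 makes exacerbation of a pre-existing condition an AE in its own right, so worsening by that route has a post-dose start and is counted. This stands. It does not clearly rescue an AE already open on the Events CRF, which the single-record rule keeps as one entry.
- **Seriousness.** The single-record rule speaks of severity, and the explicit first-start-date instruction belongs to a restricted-use form. This stands in part: for the Events CRF, the treatment of an event that becomes serious is inferred from the onset-date item and from follow-up information going onto the existing entry.
- **Other routes.** Worst laboratory shifts and the liver and CK categories (SAP 9.6.2), adjudicated events (SAP 9.5.3) and the unblinded Data Review Team (Protocol 11.3) are not tied to the onset question. A missing answer counts as treatment-emergent. This stands, and it removes laboratory examples such as a rising ALT.
- **Period by onset.** Assigning an event to the period in which it began is a legitimate convention. This stands for classification, but does not answer the case in which seriousness arises after the end-of-treatment cut-off.

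A reader might infer that anything beginning before dosing and worsening on olpasiran is never counted, that a 28-day collection window applies to all AEs, or that the treatment comparison is materially biased toward no difference. The documents support none of these. The medical-history route contradicts the first. Table 1-1 and section 5.4 contradict the second for non-serious AEs. On the third, the rule applies equally in all five blinded arms; the contrast would shrink only if the drug caused such worsening, and no size can be given.

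**Conclusion.** The concern holds in narrow form. An AE on the Events CRF before first dose, answered Yes, that increases in severity or becomes serious on treatment is excluded from both TEAE periods and from the TEAE tables. An AE open at the end of the treatment period that becomes serious in follow-up is excluded from the follow-up TEAE tables and, after the end-of-treatment cut-off, may appear in no planned serious-TEAE table.

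The number affected is probably small and cannot be derived from the documents. It depends on which definition of enrollment sites follow and on whether they enter worsening on the existing record. Any count of affected subjects, or share of cases lost, would be a guess. The conclusion assumes that the SAP 5.3 wording is programmed as written and that treatment-period tables are not rerun on the final snapshot, which the SAP does not provide for. This is an inexpensive improvement to the safety reporting and does not call the primary result into question.

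**What to change.** - **SAP 5.3:** add that an AE which started before first dose and increases in severity or becomes serious on or after it is treatment-emergent.
- **Protocol 11.4 and an Events CRF completion note:** state that such worsening, after first dose or after the End of Treatment Period Date, is entered as a new record with its own date, and use that date to assign the period. Align the exacerbation, single-record and SAE-form texts with this. The SAP clause alone is not enough, because the single record need not carry a date of worsening.
- **Enrollment:** use one definition in Protocol 5.4 and Appendix 1, so that the start of AE collection is unambiguous.
- **Data already collected:** list AEs with pre-dose onset together with their worst severity and seriousness. Do any reclassification before unblinding; after that, present the listing without reclassifying.

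Cost: slightly higher TEAE counts, a change to a protocol recording rule with its CRF note, and minor programming. No figure stated in the plan changes.
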